Imagine a virtual classroom - learners wearing VR headsets in the safety of their home are immersed in a computer-generated simulation centre. Through their avatars, they can interact from a first-person perspective with their environment, colleagues and instructors. The virtual patient has been in a car accident and the learners, by interacting with the virtual trauma bay environment, must work together to perform a primary trauma survey and resuscitate the patient. The **interactive VR** environment provides the team with real time information in a realistic environment that includes the uncertainty, noise, and time pressures of a real case. At several key points in the VR video, learners are presented with interactive decision points, and their choices determine how the rest of the video unfolds

Alternatively, imagine a second immersive environment based on high-definition **360° video** obtained from our simulation centre. Single learners, wearing a VR headset, find themselves in the resuscitation room, at the foot of the bed, leading a trauma team through the assessment and resuscitation of a patient in a virtual scenario. An example of a non-interactive VR video developed by our team for the obstetrical curriculum can be found at (<https://youtu.be/AqdwMHPe0BY>).

In both the interactive VR and 360° video experiences as well as the pre- and post-test traditional theatre-based simulations, our study will aim to measure participants' heart rate (HR), heart rate variability (HRV) and oxygen saturation levels as markers of arousal and stress responses. These will serve as a physiological indication for: 1) their comfort and change in comfort when leading scenarios and making decisions for critically ill patients in real-time and 2) their emotional engagement in their own learning throughout the immersive experiences.

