The present application is for the development and evaluation of two VR simulations (interactive VR, 360° video) applied to the context of Emergency Medicine. The aim of this pilot study is to develop two VR simulations, and to compare their effectiveness with traditional theatre-based simulations. Given the novelty of both interactive VR and 360° video simulations, our primary objective is to compare knowledge retention and application of knowledge during a paper quiz and traditional theatre-based emergency department simulations following preparation with either 360° video training or interactive VR training. The secondary objectives are to assess the usability and feasibility (resources), as well as the emotional engagement, of the above three modalities.

Methods:

Phase 1: Creation of Content: A software engineer with expertise in video-game development will be hired to develop the computer-generated emergency department in collaboration with the educators and clinicians on the team. A theatre-based trauma scenario from the current uOttawa Emergency Department curriculum will be adapted to the **VR platform**. This virtual environment will allow a team of students to manage a patient simultaneously through their avatars, from a first-person perspective. In parallel, a well-managed depiction of the same scenario will be scripted and recorded using a **360-degree HD video** camera. The recording will be made using the investigators as actors, with additional interprofessional volunteers recruited as needed. These videos will be edited and then converted to an application that can be uploaded to the Oculus® platform. Both platforms will undergo piloting for content and usability. The amount of time, money and other resources required to develop each of these scenarios will be calculated.

Phase 2: Evaluating the intervention:

Participants: 40 residents and medical students will be recruited to participate in the evaluation of the VR modules. Participants will be randomized to one of two groups (20 participants per group) – interactive VR or 360° video education. See Figure 1.

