Pre-Test: Prior to participating in one of the two educational interventions (360°-video or interactive VR), participants will complete a pre-test of their content-specific knowledge and knowledge application with respect to basic presentations to the emergency department. All participants will complete a video-recorded simulation of an emergency department case, half will complete Case A while the remaining half will complete Case B. These cases will be counter-balanced at post-test in order to account for any possible differences in case difficulty. All participants will also complete a knowledge test which will consist of approximately 20 multiple-choice questions with a mark out of 20 for a minimum score of 0 and maximum score of 20. Questions will be based on Advanced Cardiac Life Support (ACLS) guidelines and algorithms. Team performance will be recorded for subsequent scoring (see measures and analysis section below). During the traditional theatre-based simulation sessions, we will measure the learners' HR and HRV with the use of a Polar H10™ chest belt linked with a commercial capture and analysis software (EliteHRV™) program on an iPad. This will allow us to measure both arousal and stress responses, as physiological indication of the learners' emotional engagement.

Intervention: Following the pre-test, participants will either participate in the interactive VR or the 360° educational video. In each condition, the scenarios will be matched for duration, and will be followed by a debriefing session focused on the learners' comprehension of the case, their rationales for decisions, as well as closing any observed gaps in performance. UOSSC-affiliated instructors with formalized simulation and debriefing training will lead the debriefing. The learners' HR and HRV will be captured during the simulation and the debriefing sessions as a measure of engagement during the activity.

Post-Test: Two weeks after the education session, all participants will complete a post-test of their knowledge and knowledge application (matched in difficulty with pre-test), as well as lead a theatre-based simulated case. Participants who completed Case A will now complete Case B and vice versa. The sessions will be videotaped for subsequent rating of clinical and team performance. We will also capture their HR and HRV again as measures of physiological arousal and stress.

Measures and Analyses:

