This will be an equivalency study which hypothesizes that there will not be a difference in learning between 360-VR or interactive VR. The primary outcome measures for this study will be changes in knowledge and in clinical performance from pre-test to post-test. Two experienced simulation instructors will view and score the videos, blinded to the group allocation and whether the scenario is pre or post the intervention. The raters will evaluate the learners using the Ottawa GRS scale as well as a checklist of expected actions for the scenario. The raters will independently rate the videos, and their level of agreement will be calculated using an intra-class correlations coefficient. The averaged scores, as well as scores on the knowledge tests, will be submitted to separate mixed-design analyses of variance (ANOVA) with time (pre, post) as a repeated-measure and groups (interactive VR, 360° video) as a between-subject variable. Post-hoc analyses will be conducted with relevant paired or unpaired t-tests.

The secondary outcomes measures are arousal and stress responses during pre and post theatre-based simulation sessions, educational sessions, and debriefing sessions. Mean and peak HR and HRV (rMSSD, pNN50) will be submitted to separate ANOVAs, with time (pre-test, debriefing, post-test) as a repeated measure and group (interactive VR, 360° video, theatre-based) as a between-subject variable. Post-hoc analyses will be conducted with relevant paired/unpaired t-tests.

Another secondary outcome measure will be the cost-effectiveness of the education interventions, based on Levin’s cost effectiveness model⁴ applied to simulation-based education⁵. The cost categories will include equipment and materials (e.g. market price of equipment, maintenance cost), personnel costs (e.g. staff salary, volunteer time), facility costs (e.g. facility rental fee, facility maintenance), required client inputs (e.g. learner costs, opportunity costs), and other program costs (e.g. communications fees, servers for storage and retrieval of information). These will be summed into a dollar estimation for each modality, and compared using a one-way between-subject ANOVA, with group (interactive VR, 360° video) as the between variable.

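### The secondary HR/HRV ANOVA includes a theatre-based group to which nobody is randomised, and its time factor leaves out the educational session in which engagement is recorded

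*Protocol*

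**What the plan says.** **Allocation.** Protocol, Phase 2, Participants: "Participants will be randomized to one of two groups (20 participants per group"), the two being interactive VR and 360° video.

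**Where theatre simulation occurs.** Under Pre-Test, "All participants will complete a video-recorded simulation of an emergency department case". Under Post-Test, two weeks after the education session, all participants take the knowledge test again "as well as lead a theatre-based simulated case".

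**Where HR and HRV are recorded.** The Background plans physiological measurement "In both the interactive VR and 360° video experiences as well as the pre- and post-test traditional theatre-based simulations", and gives as one purpose to indicate "their emotional engagement in their own learning throughout the immersive experiences". The Intervention paragraph says the learners' "HR and HRV will be captured during the simulation and the debriefing sessions as a measure of engagement during the activity".

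**Secondary outcome.** Measures and Analyses defines it as "arousal and stress responses during pre and post theatre-based simulation sessions, educational sessions, and debriefing sessions".

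**Secondary model.** The next sentence puts mean and peak HR and HRV (rMSSD, pNN50) into separate ANOVAs "with time (pre-test, debriefing, post-test) as a repeated measure and group (interactive VR, 360° video, theatre-based) as a between-subject variable".

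**Objective.** The closing paragraph of the Background makes emotional engagement in all three modalities (interactive VR, 360° video, theatre) a secondary objective.

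**The concern.** The model names a level of the between-subject factor that the design does not create. It also omits the level of the repeated factor that bears most directly on the objective. Both are conflicts within the Protocol's own text, not detail that could be left to a SAP.

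The empty group matters because it suggests a three-way comparison of modalities that cannot be estimated between subjects. It also leaves room for a poor workaround: someone could recode the theatre sessions as an independent group, and so treat repeated measurements on the same people as if they came from different people.

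The missing session matters more. Engagement is to be measured while learners are in the assigned modality, yet the stated model has no place for those recordings. The Outcome section says the evaluation will help choose between virtual modalities partly on emotional engagement. As written, the direct comparison of interactive VR with 360° video during the session is not a planned contrast. If the factor levels are settled only after HR/HRV data have been seen by group, that comparison becomes post hoc.

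**Working it through.** **Inputs.** N = 40, in 2 groups of 20 (Phase 2, Participants). The written model has G = 3 groups and T = 3 times, and the outcome definition covers 4 sessions (both from Measures and Analyses). The counts assume complete recording.

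**Step 1: group membership.** 2 × 20 = 40 reproduces the stated sample size. That leaves 40 − 40 = 0 participants for a theatre-based group. In the same section, the primary ANOVA and the cost ANOVA both use two groups.

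**Step 2: what the written model can estimate.** It has 3 × 3 = 9 group-by-time cells. The theatre-based group would fill 3 of them and has no members, so 6 cells hold data and the cell-means design matrix has rank 6 of 9. For the group factor alone, the design matrix has 3 columns and rank 2, so the theatre-based effect cannot be estimated.

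**Step 3: sessions recorded against sessions modelled.**

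| Session | Named in outcome | HR/HRV capture planned | In time factor |
|---|---|---|---|
| Pre-test theatre | yes | yes | yes |
| Educational session (VR or 360°) | yes | yes | **no** |
| Debriefing | yes | yes | yes |
| Post-test theatre | yes | yes | yes |

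Debriefing cannot be read as covering the educational session. The outcome definition lists the two separately, and the Intervention paragraph has one follow the other.

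**Step 4: size of the omission.** Planned recordings: 40 × 4 = 160 participant-occasions. In the written model: 40 × 3 = 120. Outside it: 160 − 120 = 40, and 40/160 = 25%. This holds for each HR/HRV measure.

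**Step 5: degrees of freedom**, before any sphericity correction. Group: G − 1 and N − G. Time: T − 1 and (N − G)(T − 1). Interaction: (G − 1)(T − 1) and (N − G)(T − 1).

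| Model | Group | Time | Group × time | Cells filled |
|---|---|---|---|---|
| As written, 3 × 3 (nominal) | 2, 37 | 2, 74 | 4, 74 | 6 of 9 |
| Empty level dropped, 2 × 3 | 1, 38 | 2, 76 | 2, 76 | 6 of 6 |
| Corrected, 2 × 4 | 1, 38 | 3, 114 | 3, 114 | 8 of 8 |

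The first row cannot be obtained from this design. The second is what an analyst would get by dropping the empty level, and it still lacks the educational session.

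**The case against.** The strongest reply is that the third group is a slip of wording. Allocation is clear, the other two ANOVAs are right, and any analyst would drop a level with no members without losing a participant or changing the two-group comparison. The counts of empty cells and rank only restate that nobody is in the group; they do not measure harm. That much stands. Taken alone, the empty group would be minor, but dropping it does not bring back the omitted session or give the three-modality objective a valid analysis.

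On the omitted session, nothing says the data will be discarded. They are a named outcome, missing from one list of factor levels. The 25% is a share of planned recordings, not a loss of power for any stated test. The debriefing recording, which the Protocol also treats as a measure of engagement, stays in the model. These points limit the finding to what lies outside the stated model, but that is the immersive session itself.

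The post-hoc paired t-tests already planned could contrast modality with theatre within subjects. They are tied to the ANOVA, however, and its time factor lacks the session they would need.

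A further caution also stands. The Background describes 360° video as the more passive experience, so an HR or HRV difference during the session could reflect activity as well as emotional engagement. Adding the level makes the comparison possible; it does not settle its interpretation.

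Finally, this is a secondary outcome in a study that calls itself a pilot. That limits the weight of the point, but not its correctness.

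**Conclusion.** The concern holds. The theatre-based between-subject level has 0 of 40 participants, and the time factor covers 3 of the 4 sessions in the Protocol's own outcome definition. The missing session accounts for 25% of planned participant-occasions, assuming complete recording, and for every recording made during the VR or 360° experience.

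The consequence is limited. Without the empty level, the model still compares the two randomised groups at pre-test, debriefing and post-test, so the engagement objective is partly answered. What is lost is engagement during the session itself, and any between-subject estimate for theatre. The primary outcomes, the primary ANOVA, the sample size and the allocation are not affected. The point should be fixed, and the omitted session is the weightier part.

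**What to change.** In Measures and Analyses, keep the mixed-design ANOVA for HR/HRV and restate its factors:

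- **Group (between subjects):** interactive VR, 360° video.
- **Time (within subjects):** pre-test theatre, educational session, debriefing, post-test theatre.

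Report the between-group contrast at the educational session alongside those at debriefing and post-test, and note that the two modalities may differ in activity as well as in engagement. Keep the pre-test as a level of the repeated factor. If a baseline-adjusted model is preferred, use the pre-test only as a covariate, not in both roles.

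Any contrast of a VR modality with theatre should be within subjects and labelled exploratory. It should be stated to be confounded with order: the theatre sessions always fall before and after the intervention, and that sequence is not counterbalanced.

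For consistency, reword the Background aim of comparing the VR simulations' effectiveness with theatre-based simulation, because no arm is trained by theatre.

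The cost is protocol wording and minor analysis work. No new participants or measurements are needed, since capture during the educational session is already planned. The change should be made and dated before HR/HRV data are examined by group. The team gives up a claim of effectiveness against theatre that the design cannot support.

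### HR/HRV is recorded only during active sessions, with no resting reference and no common recording window, so debriefing-versus-theatre contrasts mix arousal with type of activity and peak HR also reflects recording length

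*Protocol*

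**What the plan says.** Under Measures and Analyses, the Protocol lists as secondary outcomes "arousal and stress responses during pre and post theatre-based simulation sessions, educational sessions, and debriefing sessions". It then states: "Mean and peak HR and HRV (rMSSD, pNN50) will be submitted to separate ANOVAs", "with time (pre-test, debriefing, post-test) as a repeated measure". The time factor has three levels, and none of them is rest.

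Phase 2 of the Methods says when the belt records:

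- The Pre-Test paragraph places the measurement inside the case: "During the traditional theatre-based simulation sessions, we will measure the" learners' HR and HRV.
- The Intervention paragraph says: "The learners' HR and HRV will be captured during the simulation and the debriefing sessions as a measure of engagement during the activity".
- The Post-Test paragraph says: "We will also capture their HR and HRV again as measures of physiological arousal and stress".

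The order of the first two steps is given, but not the interval: "Following the pre-test, participants will either participate in the interactive VR or the 360° educational video". The post-test comes two weeks after the education session, with Cases A and B exchanged.

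The only statement on length is in the Intervention paragraph, which matches the two educational scenarios for duration. Nothing is said about the length of the theatre cases or the debriefing.

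The Background gives the measures two uses: comfort, and change in comfort, when leading cases; and emotional engagement during the immersive experiences.

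**The concern.** Heart rate during an activity depends on the person's resting level that day, on what the activity demands, and on arousal. Only arousal is of interest here. Without a resting recording, the resting level cannot be separated from the rest.

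The time factor also sets leading a simulated case beside a discussion of that learning. A lower HR in the debriefing could be read as less arousal when it only reflects a different activity.

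Peak HR has a second problem. A maximum tends to grow with the time over which it is taken, so recordings of different length give different peaks even when arousal is the same.

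Emotional engagement is a secondary objective, and the Outcome section lists it among the results meant to guide the choice of modality. An analysis plan written later can define a window. It cannot supply a resting value that was never recorded.

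**Working it through.** The Protocol gives no HR SD, effect size or recording length, so there is no figure of its own to reproduce. The first two steps set its statements side by side. The others show scale under stated assumptions.

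**1. What is recorded and what is analysed**

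| Occasion | Activity | Level of the time factor? | Length controlled? |
|---|---|---|---|
| Pre-test | leading a theatre case | yes | not stated |
| Educational session | headset scenario | no | matched between arms |
| Debriefing | discussion | yes | not stated |
| Post-test | leading a theatre case | yes | not stated |
| Rest | none planned | no | none |

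The one session with controlled length is not in the analysis that compares occasions.

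**2. What each contrast contains**

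Write the value on an occasion as rest + activity demand + arousal.

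- Debriefing minus theatre case = change in rest (if on different days) + change in activity demand + change in arousal. Activity and arousal cannot be separated.
- Post-test minus pre-test = change in rest + change in arousal. The task is of the same kind and the cases are crossed over, so activity largely drops out. For peak HR, any difference in case length remains.
- Group-by-time = difference between arms in these changes. Anything common to both arms cancels. Check: a shift of 5 bpm in both arms, SD of change 10 bpm, 20 per arm, 5,000 simulated trials, gave 4.9% rejection at a nominal 5%.

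**3. Peak HR and recording length**

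Assumptions: stationary first-order autoregressive HR with constant mean, within-recording SD 8 bpm, 5-second epochs, 20,000 series. Expected peak above the mean, in bpm:

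| Correlation time | 10 min | 20 min | 30 min | 20 vs 10 min |
|---|---|---|---|---|
| 30 s | 18.0 | 20.4 | 21.7 | 20.4 − 18.0 = 2.4 |
| 60 s | 16.1 | 18.8 | 20.2 | 18.8 − 16.1 = 2.7 |

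The artefact is about 2.5 bpm. With 1-second steps and wider assumptions (SD 6 to 10 bpm, correlation time 10 to 60 s), it is 1.4 to 3.5 bpm for 20 versus 10 minutes and 2.3 to 5.3 bpm for 30 versus 10 minutes. Mean HR has no such drift.

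**4. Effect on a paired time contrast**

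For a spurious shift d, the paired t-test has noncentrality d × √n / SD of the paired difference. With d = 3 bpm:

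| n | SD 8 bpm | SD 12 bpm |
|---|---|---|
| 20 | 36% | 19% |
| 40 | 64% | 34% |

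These are rejection rates against a nominal 5%, with no true difference in arousal.

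**5. If length differed by arm**

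Suppose one arm alone carried a 2.5 bpm artefact. The noncentrality with 20 per arm is 2.5 / (SD × √(2/20)).

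- SD 8: 2.5 / 2.53 = 0.99, rejection about 16%.
- SD 12: 2.5 / 3.79 = 0.66, rejection about 10%.

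**6. Arm comparison on one occasion**

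Half-width of the 95% interval = 1.96 × SD × √(2/20): 6.2 bpm for SD 10 and 9.3 bpm for SD 15. Adjusting for a resting value with correlation r multiplies this by √(1 − r²).

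- r = 0.6 (factor 0.8): 5.0 and 7.4 bpm.
- r = 0.8 (factor 0.6): 3.7 and 5.6 bpm.

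**The case against.** The strongest reply is that the contrasts that matter most are sound. Change in comfort when leading a case is read from pre-test versus post-test, which compares like tasks with crossed cases. The comparison of modalities rests on randomised arms, where common shifts cancel. Engagement during the headset sessions concerns recordings that are matched in duration between arms. No passage says that debriefing-versus-theatre HR will be reported as an engagement result. Windows and the definition of a peak are often left to an analysis plan. The length artefact of about 2.5 bpm is also small beside an arm-comparison half-width of 6.2 to 9.3 bpm, and every input to it is assumed. Finally, the pre-test recording already serves as a same-task baseline for the post-test arm comparison, so the gain in step 6 is measured against an unadjusted analysis. What rest adds beyond that baseline has not been shown.

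Most of this stands, and it limits the point. It does not remove it. The Protocol itself makes the debriefing a level of the time factor and plans paired post-hoc tests across those levels. The missing resting recording is a matter of data collection, which an analysis plan cannot repair. A window alone could be left to that plan; it is raised here because it belongs with the same correction.

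**Conclusion.** The point holds for a secondary outcome in a self-described pilot, as a cheap improvement. With no resting reference, debriefing-versus-theatre contrasts and the time main effect cannot be read as arousal. Peak HR carries an extra dependence on recording length, about 2.5 bpm for 20 versus 10 minutes under an assumed SD of 8 bpm and correlation time of 30 to 60 s. For pre-test versus post-test, only day-to-day resting level and case length are uncontrolled.

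A reader might infer more than the document supports:

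- **That recordings are of unequal length.** The Protocol is silent on theatre and debriefing lengths. They are not fixed, but they are not stated to differ.
- **That the group-by-time test is biased.** It is affected only if length differs by arm. The debriefing is meant to close gaps in performance, so its length could depend on how each arm performed. That is possible, not stated, and the 10% to 16% in step 5 applies only in that case.
- **That posture explains a lower HR in the debriefing.** Posture is never mentioned. A difference is plausible but is an assumption.
- **That arousal carries over from the pre-test.** This needs sessions close together, and the interval is not given. It could reach the education session and debriefing, but not plausibly a post-test two weeks later.

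**What to change.** 1. With the belt already on, record about 5 minutes of seated rest at the start of each visit. If the education session falls on a separate day from the pre-test, include that visit too, or the debriefing has no rest value of its own day.
2. Analyse mean HR, peak HR, rMSSD and pNN50 adjusted for that day's rest.
3. Compute all four over one pre-specified window of equal length on every occasion, set from the shortest planned session.
4. Report debriefing-versus-theatre contrasts as descriptive. Adjusting for rest does not separate activity from arousal.

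The cost is about 5 minutes per visit: 10 minutes per participant over two visits, 15 over three. No new equipment or staff is needed. There are two drawbacks. Recording outside the window goes unused in the main comparison and may include late peaks. Rest taken just before an assessed case may contain some anticipatory arousal, so the adjustment may remove a little of the response of interest.

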Outcome: After six months, we will have developed interactive, virtual educational content for training medical students and residents in emergency medicine using two different VR modalities. These modalities will be easily scalable to other programs across the Faculty of Medicine. In addition, the evaluation phase will result in data to help support decisions regarding which virtual modalities are best suited to distanced simulation, in terms of educational effectiveness (knowledge, clinical performance and emotional engagement) and required costs. The calculations of costs associated with each modality will also allow for fact-based estimations of future investments in virtual-reality education.

Budget Request: \$50,000 for 1 year

Budget Justification:

Item	Price	Total
Computer Engineer	80,000/year, for 6 mos.	\$40,000
Research Assistant	5 hrs/week for 6 mos. X \$40.hr	\$7,200
Oculus Quest headset		\$800
Insta360 ONE X camera bundle with tripod		\$600
InstaVR app VR platform	\$199 USD/month = 270 CDN x 5 mos.	\$1350
		\$49,950

Computer Engineer: A software engineer, with expertise in computer-generation of environments for virtual platforms, will be hired on a full-time basis for a period of 6 months. During this period of time, the individual will work with the team to create an interactive VR trauma bay scenario (that can subsequently be adapted to other clinical content), as well as develop the 360° video based on recordings made by the team.

Research Assistant: The research assistant will support the team in the recruitment, scheduling, data collection, and data entry and analysis elements of the project. We will contract a skilled research assistant from DIME’s Research Support Unit, at their standard rate of \$40/hr

References

¹ Cook, David A., Ryan Brydges, Stanley J. Hamstra, Benjamin Zendejas, Jason H. Szostek, Amy T. Wang, Patricia J. Erwin, and Rose Hatala. "Comparative effectiveness of technology-enhanced simulation versus other instructional methods: a systematic review and meta-analysis." *Simulation in Healthcare* 7, no. 5 (2012): 308-320.

[figure not shown]
² Drummond D, Hadchouel A, Tesnière A. Serious games for health: three steps forwards. *Adv Simul (Lond)*. 2017;2:3. Published 2017 Feb 4. doi:10.1186/s41077-017-0036-3

³ Pasquier P, Gaudry S, Tesniere A, Mignon A. New insights into virtual medical education and assessment, Serious Games, and Digital Platforms. *Bull Acad Natl Med*. 2015;199(7):1153-1164.

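### The cost comparison applies a one-way ANOVA to one dollar total per modality, which leaves no error degrees of freedom; no per-participant cost is defined

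*Protocol*

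**What the plan says.** Under Measures and Analyses, the protocol states: "Another secondary outcome measure will be the cost-effectiveness of the education interventions". It lists five categories: equipment and materials, personnel, facility, required client inputs, and other program costs. It then fixes the outcome and the test in one sentence: "These will be summed into a dollar estimation for each modality, and compared using a one-way between-subject ANOVA". The factor in that test is the modality, at two levels.

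Other parts of the protocol also place cost at the level of the modality or scenario:

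- Phase 1 (Creation of Content): "The amount of time, money and other resources required to develop each of these scenarios will be calculated".
- Outcome: "The calculations of costs associated with each modality will also allow for fact-based estimations of future investments in virtual-reality education".
- Figure 1 lists costs and required resources, with no unit.

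The one listed category that plainly belongs to learners is "required client inputs (e.g. learner costs, opportunity costs", but no measurement per participant is described. The Budget Justification has a single engineer create the interactive VR scenario "as well as develop the 360° video based on recordings made by the team".

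**The concern.** An ANOVA needs replicate observations within each group, because their spread is the yardstick for the difference between groups. A single summed figure per modality has no replicates. The protocol therefore names an outcome and a test that do not fit together.

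The natural rescue is to treat each learner as carrying a cost. Most of the listed items (equipment, staff, facilities, servers) are bought once per modality, so this either produces no spread at all or a spread that reflects only differences between learners. Such a p-value would depend heavily on how shared development cost is assigned to the two modalities, yet it could be read as statistical evidence that one is cheaper. The Outcome section intends the cost results to inform the choice of modality and future investment, so a misreading would have consequences. In addition, the only comparison specified for an outcome called cost-effectiveness uses cost without effect.

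**Working it through.** The protocol gives no F, p or power figure for cost, so there is nothing to reproduce. The check concerns degrees of freedom and what the error term would measure.

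**Inputs from the protocol.** Groups k = 2 and one summed total per modality (Measures and Analyses); 20 participants per group (Phase 2); engineer $40,000 (budget table). The budget lines are 40,000 + 7,200 + 800 + 600 + 1,350 = $49,950, so the engineer line is 40,000 / 49,950 = 80.1% of the request.

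**1. As written.** N = 2, k = 2. Between-group df = k − 1 = 1 and error df = N − k = 2 − 2 = 0. The error mean square is 0/0. A standard ANOVA routine given one value per group returns no number for F or p.

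**2. Modality total shared equally over learners.** N = 40, so error df = 40 − 2 = 38. Every learner in an arm has the same cost, so the within-group sum of squares is 0. F is infinite and p = 0 for any non-zero difference, however small.

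**3. The five categories as replicates.** Error df = 10 − 2 = 8. However, the protocol sums the categories, and they are not exchangeable units.

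**4. Shared cost plus learner-level variation.** F is finite. The following is an illustration. Its assumptions, none given in the protocol, are that engineer cost is shared equally over 20 learners per arm, mean learner costs are equal, other shared costs do not differ, and the learner-cost SD s is $50, $100 or $200. With a fraction q of engineer cost assigned to one modality:

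- Per-learner difference: d = (2q − 1) × 40,000 / 20.
- F(1,38) = (n/2)(d/s)² = 10(d/s)².

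At q = 0.55, d = 0.10 × 2,000 = $200 per learner, or $4,000 in total. The critical F(1,38) at 5% is 4.098, so significance needs d = √0.4098 × s = 0.640s.

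| Learner SD | F at 55/45 | p | d needed for p < 0.05 | Difference in totals | Split |
|---|---|---|---|---|---|
| $50 | 160 | 3 × 10⁻¹⁵ | $32 | $640 | 50.8/49.2 |
| $100 | 40 | 2 × 10⁻⁷ | $64 | $1,280 | 51.6/48.4 |
| $200 | 10 | 0.003 | $128 | $2,561 | 53.2/46.8 |

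A 45/55 split gives the same F and p with the other modality cheaper. Under these assumptions, a shift of 1 to 3 percentage points away from an even split decides significance, while the error term carries no information about the split.

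**The case against.** The strongest reply is that zero degrees of freedom follows only from the most literal reading. The term between-subject and the learner and opportunity costs both point to costs below modality level. If that was the intent, the gap is an undefined costing unit, which an SAP or costing worksheet (not shown) might settle. Costs might also vary by session, since VR learners work in teams, 360° learners work singly, and debriefings are led by instructors. This qualifies the point but does not remove it. The same sentence sets the unit as the modality, no participant or session cost is defined, and variation between learners or sessions would still not measure uncertainty in shared development cost. An SAP could repair this only by departing from the protocol's text.

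The illustration is also open to fair criticism. The SD and the split are assumed, and nothing in the protocol suggests a near-even split; Phase 1 describes hiring the engineer mainly for the computer-generated environment, so a reversal of direction is hypothetical. The 80% is a share of the grant request, which includes research-assistant time and leaves out facility, volunteer and instructor costs. It shows that one large line is shared, not what fraction of modality cost it will be. These limits stand. The conclusion in steps 1 and 2 depends on none of them.

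Finally, Phase 1 already plans to calculate resources per scenario, and the Outcome section intends to weigh effectiveness and cost together. Both help, although the method of dividing engineer time is unstated and the specified test still uses cost alone.

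**Conclusion.** The concern holds. As written, the cost ANOVA has 0 error degrees of freedom and cannot be computed; this rests only on the protocol's own definition of the outcome and groups. Under an undefined per-participant reading it has 38, but the p-value is either degenerate or measured against variation between learners that is irrelevant to the shared costs. The F values of 10 to 160 illustrate this second problem and depend on the assumed SD and split.

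This should be corrected, but its reach is limited: a secondary outcome in a pilot, with usable cost totals and no effect on the primary learning comparison.

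**What to change.** Delete the ANOVA for cost and replace it with a descriptive comparison:

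- Report each modality's total and per-learner cost by category, with fixed costs (development, equipment) separate from per-learner costs.
- State how the engineer's time is allocated between the modalities.
- Give one-way sensitivity ranges on the main inputs, for example the developer-time split and the number of learners trained.
- Show the cost difference beside the between-group differences in knowledge and clinical performance with their confidence intervals. A cost-per-point ratio is not required.

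The minimum repair is to remove the test; the other items make the cost figures interpretable. The price is a wording change and a small spreadsheet. Development time and money per scenario are already to be calculated, but the engineer's hours would have to be logged by modality. All that is lost is a p-value with no useful meaning.
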